1. BACKGROUND

1.1. Myelofibrosis

The term myelofibrosis (MF) includes both primary myelofibrosis (PMF) and post-polycythemia vera/essential thrombocythemia myelofibrosis (post-PV/ET MF) (Tefferi 2011). MF is currently classified as a chronic myeloproliferative neoplasm (MPN) and is characterized by clonal proliferation of pluripotent hematopoietic stem cells and abnormal cytokine expression (Tefferi 2011). Patients with MF typically present with anemia, marked splenomegaly and profound constitutional symptoms (night sweats, pruritus, early satiety, bone pain, cough, fever, etc.). In addition, some patients might display thrombocytopenia, leucopenia, thrombocytosis, leukocytosis, and non-hepatosplenic extramedullary hematopoiesis (EMH) (Tefferi 2011). Current drug therapy for MF, such as erythropoiesis stimulating agents (ESAs), hydroxyurea and JAK inhibitors have not been shown to influence survival and are often used for palliative purposes only (Tefferi 2011). Allogeneic stem cell transplantation (ASCT), which is so far the only curative option, carries a high treatment-related mortality and morbidity (Tefferi 2011).

The International Prognostic Scoring System (IPSS), used for risk stratification in PMF, uses risk factors assessed at time of diagnosis: age >65 years, constitutional symptoms, hemoglobin < 10 gm/dL, leukocyte count $>25 \times 10^9/L$ and peripheral blood blasts $\geq 1\%$ (Tefferi 2011). Subsequently, the IPSS prognostic variables were used to devise a dynamic IPSS (DIPSS) that can be utilized at any point during the disease (Tefferi 2011). Most recently, DIPSS was further revised to DIPSS-plus by the incorporation of 3 additional IPSS/DIPSS-independent risk factors, including red cell transfusion need, platelet count $<100 \times 10^9/L$, and unfavorable karyotype (Tefferi 2011); the latter includes complex karyotype or sole or 2 abnormalities that include +8, -7/7q-, i(17q), inv(3), -5/5q-, 12p-, or 11q23 rearrangement. The 8 DIPSS-plus risk factors are currently used to define low (no risk factors), intermediate- 1 (1 risk factor), intermediate-2 (2 or 3 risk factors), and high (≥ 4 risk factors) risk groups with respective median survivals of 15.4, 6.5, 2.9, and 1.3 years (Tefferi 2011). Patients with MF can progress into blast phase disease (BP-MF), defined by the same criteria used by WHO for acute myeloid leukemia (AML) (i.e. 20% or more blasts in the peripheral blood or bone marrow). Some patients with MPN share certain morphologic features with those with myelodysplastic syndromes (MDS). The WHO classifies such cases as MDS/MPN overlap and their clinical features are similar to patients with MF (i.e. severe anemia, splenomegaly, leukocytosis and thrombocytosis).

1.2. Telomeres and Telomerase Inhibition

Telomeres consist of tandem repeats of the DNA sequence TTAGGG, forming a T-loop structure to cap the ends of all mammalian chromosomes. Capping prevents chromosomal fusion and prevents their ends from being misinterpreted as DNA double-strand breaks (McEachern 2000). Telomeres shorten approximately 50–120 nucleotides (nt) at each cell division (Harley 2002; Harley 1997). When telomeres get critically short, they can no longer cap the telomere ends, thus destabilizing the T-loop and exposing a 3' overhang which triggers a DNA damage signal, ultimately resulting in senescence, terminal differentiation, or apoptosis. Telomere loss is prevented by the presence of the enzyme telomerase, which consists of two essential

components: the human telomerase RNA template (hTR) and the human telomerase reverse transcriptase (hTERT) catalytic subunit. Telomerase counters telomere loss by the addition of TTAGGG repeats to the chromosome ends ([Harley 1997](#)).

Normal somatic cells have relatively long telomeres (~9–12 kilobases) ([Rufer 1999](#)) and typically do not express detectable levels of telomerase. In contrast, telomerase activity has been detected in 80–90% of cancers tested to date, and is key to cell immortalization through maintenance of telomere length (TL) ([Shay 1997](#)). Most tumors have shorter telomeres, compared to their normal tissue counterparts, in spite of telomerase activation. These two characteristics make telomerase a promising therapeutic target for cancer.

1.3. Imetelstat

Imetelstat (GRN163L) is a covalently-lipidated 13-mer thiophosphoramidate oligonucleotide that acts as a potent specific inhibitor of telomerase. Telomerase inhibition leads to the loss of a cancer cell's ability to maintain TL, resulting in cell-cycle arrest, apoptosis, or senescence. The mechanism of action of imetelstat is not an antisense-based approach. Imetelstat does not cause down regulation of mRNA encoding either the hTR or hTERT subunits of telomerase, nor does it affect RNase H activity, which typically causes degradation of mRNA when it is targeted by an antisense phosphoramidate oligonucleotide. Imetelstat binds with high affinity to hTR and is a competitive inhibitor of telomerase enzymatic activity ([Asai 2003; Herbert 2005](#)). Studies have shown that treatment of various cancer cells with imetelstat in vitro increases their sensitivity to radiation, decreases their clonogenic potential, and results in altered expression of stem-cell related genes ([Stewart 2010](#)) ([Harley 2008](#)).

1.3.1. Nonclinical Pharmacology

1.3.1.1. Efficacy Studies

Data from nonclinical efficacy studies have shown that imetelstat inhibits telomerase in tumor cells and compromises cancer cell viability in vitro. Imetelstat has broad tumor growth inhibition activity in multiple xenograft models, including non-small cell lung, breast, colorectal, pancreatic, glioblastoma multiforme (GBM), myeloma, neuroblastoma, hepatic and ovarian cancers.

1.3.1.2. Effects on Cancer Stem Cells

Numerous studies have identified a relatively rare subpopulation of tumor-initiating cells (TICs), also termed cancer stem cells (CSCs), in multiple cancer types. CSCs are distinct from the bulk tumor cell population, yet share the properties of increased telomerase activity (TA) and short telomeres, making CSCs of multiple tumor types promising targets for telomerase inhibition. In vitro studies have demonstrated that imetelstat inhibits telomerase, and is effective in targeting CSCs from myeloma, melanoma, breast, pancreatic, pediatric glioma, neuroblastoma, prostatic, lung and glioblastoma multiforme tumor types ([Joseph et al. 2010b; Marian et al. 2010a](#)). Treatment of CSCs with imetelstat results in increased apoptosis, induction of senescence, and inhibition of proliferation, sphere formation, and clonogenicity. In vivo studies demonstrated that imetelstat is able to significantly inhibit CSC-mediated tumor engraftment and growth in

breast, pancreatic, glioblastoma, neuroblastoma, and myeloma xenograft models (Joseph et al. 2010a; Hochreiter 2006; Shammas 2008; Dikmen 2009; Castelo-Branco 2011; Marian 2010b).

1.3.2. Nonclinical Safety Studies

Imetelstat was evaluated in a broad range of toxicology studies to support its use as a systemically-delivered anticancer agent in humans. The general toxicology of imetelstat was assessed in rodents and non-human primates. Imetelstat nonclinical safety studies were carried out in mice, rats, rabbits, and cynomolgus monkeys. Support for the proposed clinical dose and schedule is based primarily on the repeat-dose studies in mice (dosed twice weekly for 26 weeks) and cynomolgus monkeys (dosed once weekly for 9 months).

Toxicities generally fit into two main categories: (1) those related to plasma concentrations of imetelstat, reflecting interactions with blood components, and (2) those reflecting tissue deposition and associated inflammatory effects, as were evident from histopathology evaluations.

Toxicities observed with imetelstat treatment included cytopenias, complement activation, and coagulation abnormalities. Complement activation and coagulation abnormalities were related to plasma concentrations of imetelstat. The etiology of the cytopenias is not clear; a direct effect on hematopoietic progenitor cells cannot be excluded.

Early intravenous (IV) bolus range-finding studies helped define the high-dose toxicity profile and repeat-dose studies characterized the full range of potential target organs for imetelstat-related adverse effects. At high doses in rodents (i.e., ≥ 30 mg/kg IV bolus), effects on hematology and coagulation parameters were observed, including elevated activated partial thromboplastin time (aPTT), hemorrhage, and decreased platelet and red blood cell pools. The occurrence of peripheral cytopenias, most notably thrombocytopenia, was sometimes accompanied by decreases in red blood cell (RBC) parameters and mild anemia. In non-human primates, hematological effects (decreases in RBC parameters and platelets at doses ≥ 15 mg/kg) were present but to a lesser extent than those seen in rodents. In ex vivo colony-forming assays using human bone marrow progenitors, imetelstat did not significantly inhibit erythroid or myeloid colony number (although colony morphology was compromised at 15 μ M), but megakaryocyte colony growth was inhibited at ≥ 3.75 μ M (50% inhibitory concentration [IC_{50}] ~ 5 μ M).

Inhibition of coagulation (aPTT prolongation) and activation of complement pathways (increased plasma levels of Bb and C5a split products and decreased total hemolytic complement [CH_{50}]) were noted. These effects were reversible and similar to acute blood level-related toxicities seen with other polyanionic oligonucleotides. There was no clinical evidence of clotting abnormalities in monkeys at relatively high doses that produced over 3-fold increases in aPTT.

Severe complement-mediated adverse reactions were noted in some of the monkey dose-finding studies; however chronic complement activation at doses ≤ 15 mg/kg did not result in any adverse constitutional outcomes. Similar to other oligonucleotides in this class, imetelstat-mediated activation of the alternative complement pathway is believed to stem from binding to an inhibitory complement protein (Factor H), which, if sufficiently depleted, initiates an activation cascade with the formation of biologically active split products culminating in

hemodynamic changes (mainly hypotension). In monkeys, this may result in significant cardiovascular toxicity. In the case of imetelstat, the threshold blood level for complement activation is approximately 200 µg/mL. Toxicokinetic analyses confirmed that these acute effects are reversible after 24 hours and can be managed by adjusting the dose and duration of infusion of imetelstat.

Administration of imetelstat intravenously to monkeys at doses of up to 15 mg/kg over 2 hours once weekly for 9 months was well tolerated. Data from studies in rats suggested that imetelstat was taken up by many tissues, primarily liver, kidneys and, to a lesser extent, the spleen and bone marrow; these are the target organs for histopathologic alterations. Microscopic examination of tissues revealed mild to moderate changes in the kidney (mesangial thickening, glomerulonephritis/sclerosis, deposition in interstitium, renal tubular hemorrhage, protein casts, and regeneration), liver (telangiectasis and deposition in Kupffer cells), uterus (atrophy of the endometrium), choroid plexus (minimal lymphoid follicle formation and mononuclear cellular infiltration), and general systemic arteritis including at the injection site at doses starting at 5 mg/kg. The observations in the kidney did not show signs of reversibility in the recovery group animals; however, it is not unusual for such inflammatory lesions to persist for several months in monkeys. The endometrial atrophy was only noted after 9 months of chronic dosing at 15 mg/kg and was absent in the recovery animals. The remaining morphological changes in the liver and the inflammatory vasculitis (choroids plexus and systemic arteritis) showed signs of resolution in the recovery group animals.

Most of these histological findings are thought to be due to pro-inflammatory activity common to many oligonucleotides and derived from a programmed physiological reaction of the body to their foreign nucleic acid structure and are heightened when the molecule is chemically modified to inhibit degradation by endogenous nucleases. In general, the changes observed in the groups that received imetelstat at doses up to 15 mg/kg were of limited severity and were not associated with any tissue degeneration or other alterations that would suggest compromised organ function. Most changes showed evidence of recovery after a 14-week drug-free period.

Imetelstat was not teratogenic in mice or rabbits following bolus or 2-hour continuous intravenous (IV) infusion of 30 mg/kg. In rabbits, embryo-lethality was noted as increased post-implantation loss at 30 mg/kg due to an increase in early resorptions, resulting in higher incidence of litter loss at this dose level that correlated to a decrease in litter size and viable fetuses.

Additional findings from nonclinical studies that may predict the safety of the clinical dose include: (1) absence of effects on cardiovascular (human ether-à-go-go related gene [hERG] inhibition, electrocardiogram [ECG]), respiratory, and neurological function, and (2) absence of genetic toxicity in tests for mutagenicity and clastogenicity.

Please refer to the Imetelstat Investigator's Brochure (IB) for further details.

1.3.3. Clinical Experience with Imetelstat

[Table 1](#) and [Table 2](#) summarize all clinical trials with imetelstat initiated by Geron to date.

A total of 491 patients have been enrolled in Geron Phase I and II imetelstat clinical trials of which 374 received imetelstat either as a single agent or as combination therapy.

Six Phase I studies have been initiated since 2005, of which three were single-agent studies and three were combination studies. The study designs and status are summarized below and presented in [Table 1](#). A total of 183 patients were treated with imetelstat in Phase I; enrollment and study treatment has been completed and the databases locked for all six studies.

In Phase II clinical trials, imetelstat was investigated as a single agent in CP14B015 (ET/PV), as single-agent or combination therapy in CP14B013 (multiple myeloma [\pm lenalidomide]) and CP14B012 (NSCLC [\pm bevacizumab]), and as combination therapy in CP14B014 (MBC [paclitaxel \pm bevacizumab]). As of 21 May 2013, a total of 191 patients were treated with imetelstat in Phase II ([Table 2](#)).

Table 1: Phase I Clinical Trials with Imetelstat

Protocol Number	Protocol Title	Patients Enrolled	Patients Treated (Data Cut-off Date)	Dose and Schedule of Imetelstat	Key Study Endpoints	Study Status
Single Agent Trials						
CP14A004	A Phase I Sequential Cohort, Dose Escalation Trial to Determine the Safety, Tolerability, and Maximum Tolerated Dose of Weekly Administration of GRN163L in Patients with Refractory or Relapsed Multiple Myeloma	20	20 (Locked 15Nov2010)	3.2, 4.8, 6.0, 7.2 mg/kg over 2 hours weekly; 6.0 mg/kg on Days 1, 8 every 21 days.	Primary : Safety, tolerability, MTD Secondary : PK, anti-tumor activity, pharmacodynamics	Completed
CP04-151	A Phase I/II, Sequential Cohort, Dose Escalation Trial to Determine the Safety, Tolerability, and Maximum Tolerated Dose of Weekly Administration of GRN163L in Patients with Refractory or Relapsed Chronic Lymphoproliferative Disease	28	28 (Locked 15Feb2011)	20, 40, 80, 160, and 240 mg/m ² over 6 hours weekly; 160 and 200 mg/m ² over 2 hours weekly; 200 mg/m ² over 2 hours on Days 1 and 8	Primary : Safety, tolerability, MTD Secondary : PK, anti-tumor activity, pharmacodynamics	Completed
CP05-101	A Phase I, Sequential Cohort, Dose Escalation Trial to Determine the Safety, Tolerability, Maximum Tolerated Dose, and Optimal Infusion Duration of Weekly Administration of GRN163L in Patients with Refractory or Relapsed Solid Tumor Malignancies	75	75 (Locked 21Mar2011)	0.4, 0.8, 1.6, 3.2, 4.8 mg/kg over 2 hours weekly; 4.8, 6.0, 7.5, 9.4, 11.7 mg/kg on Days 1, 8 every 21 days; 9.4, 11.7 mg/kg once every 28 days	Primary : Safety, tolerability, MTD Secondary : PK, anti-tumor activity, pharmacodynamics	Completed
Combination Trials						
CP14A005	A Phase I Sequential Cohort, Dose Escalation Trial to Determine the Safety, Tolerability, and Maximum Tolerated Dose of Weekly Administration of GRN163L in Combination with Paclitaxel and Carboplatin in Patients with Advanced or Metastatic Non-Small Cell Lung Cancer	27	27 (Locked 15Oct2010)	3.2 mg/kg over 2 hours weekly; 3.2 mg/kg over 2 hours once every 21 days; 3.2, 4.8, 6.0 and 7.5 mg/kg on Days 1, 8 every 21 days.	Primary : Safety, tolerability, MTD Secondary : PK, anti-tumor activity	Completed
CP14A011	A Phase I Study of GRN163L in Combination with Bortezomib and Dexamethasone in Patients with Relapsed or Refractory Multiple Myeloma	9	9 (Locked 15Dec2010)	160, 200 mg/m ² over 2 hours Days 1, 8 every 21 days	Primary : Safety, tolerability Secondary : PK, anti-tumor activity	Completed
CP14A010	A Phase I/II Study of GRN163L in Combination with Paclitaxel and Bevacizumab in Patients with Locally Recurrent or Metastatic Breast Cancer	24	24 (Locked 28Mar12)	160, 240, 300, 375 mg/m ² Days 1, 8, 15 every 28 days; 300 and 375 mg/m ² Days 1, 15 every 28 days; 300 mg/m ² Day 8 every 28 days.	Primary : Safety, tolerability Secondary : PK, anti-tumor activity	Completed

Table 2: Phase II Trials with Imetelstat

Protocol Number	Protocol Title	Patients Enrolled	Patients Treated	Dose and Schedule of Imetelstat	Key Study Endpoints	Study Status
Randomized Trials						
CP14B012	A Randomized Phase II Study of Imetelstat as Maintenance Therapy after Initial Induction Chemotherapy for Advanced Non-Small Cell Lung Cancer (NSCLC)	116	114 (Locked 19Sep2013)	9.4 mg/kg over 2 hours on Days 1,8 every 21 days	Primary : PFS Secondary : Safety, tolerability, ORR	Completed
CP14B014	A Randomized Phase II Study of Imetelstat (GRN163L) in Combination with Paclitaxel (With or Without Bevacizumab) in Patients with Locally Advanced or Metastatic Breast Cancer	166	161 (Locked 10Dec2012)	300 mg/m ² on Day 1 every 21 days	Primary : PFS Secondary : Safety, ORR, clinical benefit rate	Completed (early termination)
Single-Arm Trials						
CP14B013	A Phase II Trial to Determine the Effect of Imetelstat (GRN163L) on Patients with Previously Treated Multiple Myeloma	13	13 (Locked 20Nov2014)	9.4 mg/kg over 2 hours on Days 1,8 every 28 days	Primary: Improvement in response Secondary: Safety, tolerability, PFS, circulating myeloma CSCs	Completed
CP14B015	A Phase II Trial to Evaluate the Activity of Imetelstat (GRN163L) in Patients with Essential Thrombocythemia or Polycythemia Vera who Require Cytoreduction and Have Failed or Are Intolerant to Previous Therapy, or who Refuse Standard Therapy	20	20 (Locked 06Apr2015)	7.5 -11.7 mg/kg over 2 hours weekly or as needed based on hematologic response	Primary : Hematologic response (ET), Hematocrit (PV) Secondary : Safety, tolerability, duration of hematologic response, molecular response, histologic response at 2 years, on study, phlebotomy rate (PV)	Completed

1.3.4. Safety Experience

The overall summary of clinical safety for imetelstat is primarily based on the 374 imetelstat treated patients in all 10 Geron sponsored Phase I and II trials to date. Where relevant, additional clinical safety information (e.g., from investigator-sponsored trials) is incorporated. For additional details, refer to the IB. A summary of clinical safety is provided below.

1.3.4.2. Coagulation Changes

In the Phase I imetelstat trials in which serial aPTT was measured following infusion, transient aPTT prolongations were observed in all patients which, at doses ≥ 3.2 mg/kg and 160 mg/m², were as high as Grade 3. Resolution to Grade 1 or normal limits was within 24 hours.

Nonclinical studies suggest that aPTT prolongation is correlated with plasma concentrations of imetelstat. PT prolongations occurred infrequently and the majority was Grade 1. In the Phase II trials, aPTT and PT were not routinely measured. No bleeding events associated with coagulation abnormalities were reported in these trials.

1.3.4.3. Infections

Infections are frequently reported across all imetelstat trials, with an overall incidence of 43.0%. The most frequently reported events are urinary tract infection and upper respiratory tract infections.

Most patients had normal neutrophil counts proximal to the infection episodes.

Febrile neutropenia is infrequent and significant infections attributed to imetelstat associated with Grade ≥ 3 neutropenia have not been reported.

On 11 March 2014, the United States Food and Drug Administration (U.S. FDA) issued Geron a full clinical hold citing lack of evidence of reversibility of hepatotoxicity, risk for chronic liver injury, and lack of adequate follow up in subjects who experienced hepatotoxicity. All subjects enrolled in Geron-sponsored clinical trials permanently discontinued imetelstat treatment and enrollment of new subjects to clinical trials was not allowed. Continued safety surveillance was implemented as part of an extended hepatic safety follow-up period of all subjects in ongoing Geron-sponsored trials who had liver biochemistry abnormalities and/or hepatic adverse events that first appeared during imetelstat treatment, or worsened from baseline during treatment, and were continuing at the time subjects' discontinued imetelstat treatment. Reversibility of these abnormalities and/or hepatic adverse events back to normal or baseline levels after discontinuing imetelstat were assessed. Data were collected from subjects who discontinued imetelstat treatment as a result of the clinical hold, as well as those who discontinued for any reason and met safety follow-up criteria prior to the clinical hold. Following a complete response submitted by Geron, the clinical hold was lifted by the U.S. FDA on 31 October 2014.

On 12 March 2014, the then sponsor-investigator for Study MC1285 was issued a partial clinical hold by the FDA. The safety issues cited by the FDA for the partial clinical hold included a safety signal of hepatotoxicity identified in clinical trials of imetelstat and whether this hepatotoxicity was reversible. Previously enrolled subjects who were deriving clinical benefit according to the principal investigator were allowed to continue treatment with imetelstat but no new subjects may be registered. Following a complete response submitted by the sponsor-investigator to the FDA, this partial clinical hold was lifted by the FDA on 11 June 2014.

Emergent hepatobiliary data continues to be monitored on an ongoing basis and third party hepatology experts will be consulted as necessary to continue to refine the understanding of this signal as data emerge.

1.3.4.5. Infusion Reactions

Oligonucleotides have been previously reported to cause complement activation and related infusion reactions with the potential to cause non-complement-related hypersensitivity reactions.

In the Phase II trials where all patients had routine prophylaxis, 19.4% of imetelstat-treated patients had an infusion reaction. The events are sporadic and a patient may not necessarily experience a subsequent event with successive infusions. Infusion reactions are generally mild to moderate in severity but symptoms and signs may occasionally be Grade 3 or 4 (incidence 3%) in severity. Reactions may be more frequent or severe with imetelstat dose levels exceeding 9.4 mg/kg. Reactions may be ameliorated, but are not always prevented, by required premedication with corticosteroids, diphenhydramine, and/or acetaminophen.

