7.2. Pre-Medication

In Phase I studies, some patients experienced infusion-related reactions to imetelstat, including but not restricted to allergy/hypersensitivity reaction (e.g., rash, fever, urticaria, dyspnea, bronchospasm, chills/rigors, myalgias, headache, fatigue, nausea and/or vomiting) during or within 24 hours of an infusion. Reactions were sporadic in nature and did not occur at a higher frequency with the first administration of imetelstat. These reactions were usually mild to moderate and generally resolved with slowing or interruption of the infusion and with supportive care (diphenhydramine, corticosteroids, and/or IV saline). The mechanism is not entirely clear but may involve complement activation. (See Section 8 for the Infusion reaction guidelines and [Appendix E](#).)

All patients will require premedication with diphenhydramine (25–50 mg, PO or IV) and hydrocortisone (100 mg PO or IV) or equivalent before receiving imetelstat.

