5. SAFETY

Safety will be analyzed using the incidence and severity of adverse events and laboratory tests based on the all treated analysis set.

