5.1. Adverse Events

The verbatim terms used in the eCRF by investigators to identify AEs will be coded using the Medical Dictionary for Regulatory Activities (MedDRA). The severity of adverse events is assessed in National Cancer Institute (NCI) common terminology criteria for adverse events (CTCAE) Version 4.0.

Treatment-emergent AEs will be defined as those events that 1) occur on or after the first dose of study drug, through the treatment phase, and for 30 days following the last dose of study drug or until subsequent anti-cancer therapy if earlier; 2) any event that is considered study drug-related regardless of the start date of the event; or 3) any event that is present at baseline but worsens in severity or is subsequently considered drug-related by the investigator.

An overview summary table of treatment-emergent AEs will be provided, including drug related AEs, CTCAE grade ≥ 3 AEs, serious AEs, and deaths.

Treatment-emergent AEs will be summarized by system organ class and preferred terms. For each treatment-emergent adverse event, the percentage of subjects who experience at least 1 occurrence of the given event will be summarized. Tables will be sorted by frequency in incidence (the highest to lowest incidence) in the total column. The same summary will be provided for the treatment-emergent AEs with CTCAE grade ≥ 3 , treatment-emergent AEs considered related to study treatment, and serious treatment-emergent AEs.

A summary of the number of subjects who discontinued study treatment because of 1 or more AEs by system organ class and preferred term will be provided. This table includes AEs leading to discontinuation of study treatment for those subjects indicated as having discontinued study treatment due to an adverse event on the end of treatment eCRF page.

Treatment-emergent bleeding events will be identified using standardized MedDRA queries (SMQs) by matching the event terms in SMQ "HAEMORRHAGES" and the first SMQ subcategory "HAEMORRHAGE TERM (EXCL LABORATORY TERMS)." The number of subjects with treatment-emergent bleeding events will be summarized for each treatment arm.

A listing of all adverse events will be provided.

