5.4. Other Safety Tests

ECOG performance status, physical exam and infusion reaction will be listed separately by cycle.

REFERENCES

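### Infusion reactions, a named drug risk, are only listed by cycle: the SAP plans no pooled incidence by worst grade and arm, and no rate per infusion given

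*Protocol*

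**What the plan says.** Protocol 1.3.4.5 reports the earlier Phase II experience: "In the Phase II trials where all patients had routine prophylaxis, 19.4% of imetelstat-treated patients had an infusion reaction", and adds that "symptoms and signs may occasionally be Grade 3 or 4 (incidence 3%) in severity". Section 7.2 requires premedication for every patient and says of the Phase I reactions: "Reactions were sporadic in nature and did not occur at a higher frequency with the first administration of imetelstat". Table 12 gives infusion reactions their own grading and management guidance, and Table 11 handles allergic reactions separately.

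The SAP mentions infusion reactions by name once, in 5.4: "ECOG performance status, physical exam and infusion reaction will be listed separately by cycle". SAP 3.3 likewise plans only a listing of exposure; the number of infusions is not summarised.

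The general safety analysis is broader. SAP 5 states: "Safety will be analyzed using the incidence and severity of adverse events and laboratory tests based on the all treated analysis set". In SAP 5.1, treatment-emergent events are tabulated by system organ class and preferred term, and for each event "the percentage of subjects who experience at least 1 occurrence of the given event will be summarized". Further tables follow: "The same summary will be provided for the treatment-emergent AEs with CTCAE grade" 3 or above, for related events and for serious events, plus a table of events leading to discontinuation. SAP 5.1 also defines a grouped set of terms for bleeding and counts subjects with such events by arm. It does nothing comparable for infusion reactions.

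**The concern.** Safety and tolerability in each arm is a secondary objective, and this is one of the risks the protocol knows about in advance. Two features of the planned tables make them a poor measure of it.

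The first is scatter. The same clinical event can enter the database as an infusion reaction (Table 12), as an allergic reaction (Table 11), or as component symptoms such as rash, fever, chills or dyspnea (7.2). These code to different preferred terms and organ classes. Protocol 10.3.1.1 prefers a diagnosis, but asks for separate entries when the signs cannot be put together as one diagnosis or syndrome. Several of the symptoms in 7.2 (fever, chills, myalgia, headache, fatigue, nausea, vomiting) also appear in 1.3.4.7 as constitutional symptoms within a few days of dosing. A preferred-term table has no onset window and cannot separate the two.

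The second is the denominator. A patient counts once if any reaction occurs. The protocol calls reactions sporadic and not concentrated at the first dose, so a patient who receives more infusions has more chances to have one. Arms with different schedules can then show different percentages at the same risk per infusion.

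At stake is whether the report can give, from a pre-specified analysis, one figure for the frequency and severity of infusion reactions in each arm.

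**Working it through.** **1. The plan's own figure.** Section 1.3.4.5 gives 19.4% without a denominator. Section 1.3.3 says "a total of 191 patients were treated with imetelstat in Phase II".
- 37/191 = 19.37%, which rounds to 19.4%; no other count out of 191 does.
- No whole count gives 19.4% out of 374 (all treated, section 1.3.4) or out of 308 (sum of the treated column of Table 2: 114 + 161 + 13 + 20).
- 3% of 191 corresponds to 5 or 6 patients.

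The figure is reproduced, but the use of 191 is an inference.

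**2. Scheduled infusions over the nine core cycles** (length from 8.1; schedules from 7.1.1.1 to 7.1.1.5), with no escalation, reduction, hold or early stop:
- Arm A: 9 × 1 = 9, over 189 days
- Arm B: 3 + 8 × 1 = 11, over 189 days
- Arms E, F and G, Cycle 2 criteria met: 9 × 1 = 9, over 252 days
- Arm F, criteria not met (Tables 7 and 8): 2 × 1 + 2 × 2 + 5 × 3 = 21, over 252 days
- Arm D: 9 × 4 = 36, over 252 days

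The largest ratio is 36/9 = 4.0. Per unit time, Arm D against Arms E, F and G is (4/28)/(1/28) = 4.0. Arm D against Arm A is (4/28)/(1/21) = 3.0, because the cycle lengths differ.

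**3. Effect on the percentage of patients.** Assume a constant, independent risk r per infusion, the same in every arm. The documents give no value for r, so a range is shown. The expected share with at least one reaction over n infusions is 1 − (1 − r)^n.

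| Schedule | n | r = 1% | r = 2% | r = 3% |
|---|---|---|---|---|
| Arm A | 9 | 9% | 17% | 24% |
| Arm B | 11 | 10% | 20% | 28% |
| Arm F, criteria not met | 21 | 19% | 35% | 47% |
| Arm D | 36 | 30% | 52% | 67% |

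At r = 2%, for example, 1 − 0.98^9 = 0.17 and 1 − 0.98^36 = 0.52: a three-fold difference from infusion count alone. The same point without choosing r: if 19.4% of patients react over some number of infusions, four times as many gives 1 − 0.806^4 = 57.8%, and three times as many gives 1 − 0.806^3 = 47.6%.

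**4. Precision of a pooled table.** Exact (Clopper-Pearson) 95% intervals near a rate of 19.4%:
- 2/11: 2.3% to 51.8%
- 5/25: 6.8% to 40.7%
- 16/80: 11.9% to 30.4%

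The 80 is the number enrolled. Arm sizes at closure are not given, so 11 and 25 are the stage 1 and one-stage design sizes in protocol 16.1.

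**The case against.** A reader might infer that the trial will report no incidence or severity of infusion reactions, or cannot say how often they occurred. The documents do not support that. A reaction recorded under its diagnosis enters the SAP 5.1 tables, including those for Grade 3 or higher, related and serious events and discontinuations. Protocol 16.4.1 also asks for the maximum grade of each type of event per patient, although section 16 says the SAP will supersede the protocol's analyses. Counts could be derived by hand from the listings in SAP 3.3 and 5.4. What is missing is a planned summary, not the information.

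A reader might also take 19.4% as a benchmark. Section 1.3.4.5 gives it as background, with no threshold, denominator or case definition, and it comes from trials in other diseases, doses and combinations. A pooled table here would not guarantee a like-for-like comparison.

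The extent of scatter is not shown. The rule in 10.3.1.1 limits it, and Tables 11 and 12 govern dose modification and management rather than recording.

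The four-fold spread is a starting-schedule figure. Arm D patients may stop early or change schedule, other arms may increase frequency, and Table 12 ends treatment after severe reactions. Constant risk is not established either: section 1.3.4.5 says reactions may be more frequent above 9.4 mg/kg, and Arms E and G start at 7.5 mg/kg. The arms are non-randomised and evaluated independently, so comparing them is not an objective.

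All of this stands as a limit on the size of the point. It does not supply a pooled definition, an onset window or an infusion denominator. Uncertainty about actual infusion counts is itself a reason to summarise them.

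**Conclusion.** The point holds as a gap in the planned summary. Infusion reactions by name are only listed, exposure is only listed, and the preferred-term tables provide neither a pooled incidence by worst grade and arm nor a rate per infusion. Those tables can undercount the risk when reactions are recorded under different terms; by how much cannot be judged from the documents.

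The dependence on infusion count is up to four-fold on starting schedules over nine cycles, enough to move an expected patient percentage from 17% to 52% at an assumed 2% per infusion. That is an illustration resting on a constant, equal and independent risk and on uninterrupted schedules; it is not a forecast for this trial.

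The improvement is worthwhile and inexpensive. No primary result is affected.

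**What to change.** In SAP 5.1 (beside the bleeding summary) or 5.4, before the analysis:

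- Fix a grouped list of infusion-reaction terms covering infusion, allergic and hypersensitivity reactions and the component symptoms in protocol 7.2, together with the reactions already destined for the 5.4 listing.
- Fix an onset window consistent with the 24-hour description in 7.2. If only dates are available, use the infusion day and the day after. State how partial onset dates are treated, since SAP 2.3 can move an event with a missing day onto the first dosing date and so into the window.
- Add one table, by arm and overall, in the all treated set: n (%) of subjects with at least one reaction with an exact 95% interval, worst grade, and reactions per 100 infusions actually given.
- Summarise the number of infusions given by arm.
- Report stopped or interrupted infusions only if they were captured; the documents do not say that they were.

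Keep the listing, and present 19.4% and 3% as context without a formal comparison.

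The cost is some SAP wording, prior agreement on the term list, and one extra table from the dosing, adverse event and infusion-reaction data that the SAP already lists. Nothing changes for patients. Arm-level estimates will be imprecise (2/11 runs from 2% to 52%), and the table should say so.
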